#### 7.1.1. Endpoint / Variables

Proportion of participants with plasma HIV-1 RNA  $\geq$  50 copies/mL as per Food and Drug Administration (FDA) Snapshot algorithm at Month 12.

#### 7.1.2. Summary Measure

Number of subjects and percentage of participants with HIV-1 RNA ≥50 c/mL at Month 12 (defined by the US FDA snapshot algorithm) will be provided by treatment group.

#### 7.1.3. Population of Interest

The primary efficacy results will be based on the Intent-To-Treat Exposed population, unless otherwise specified.

#### 7.1.4. Strategy for Intercurrent (Post-treatment selection) Events

As defined by the Snapshot algorithm, HIV-1 RNA  $\geq$  50 c/mL is determined by the last available HIV-1 RNA measurement while the participant is on treatment within the analysis visit window of interest.

Participants without on-treatment HIV-1 RNA data for the visit of interest and who discontinue treatment for reasons not related to adverse event while having HIV-1 RNA  $\geq$  50 c/mL at time of discontinuation or who change study treatment not permitted per protocol before the analysis window are classified as having HIV-1 RNA  $\geq$  50 c/mL.

Full details of the snapshot algorithm are defined in Appendix 9: Snapshot Algorithm Details.

#### 7.1.5. Statistical Analyses / Methods

Details of the planned displays are provided in Appendix 12: List of Data Displays and will be based on GSK data standards and statistical principles.

Unless otherwise specified, endpoints / variables defined in Section 7.1.1 will be summarised using descriptive statistics, graphically presented (where appropriate) and listed.

#### 7.2. Secondary Efficacy Analyses

#### 7.2.1. Endpoint / Variables

The secondary efficacy endpoints for the study are listed below:

- Proportion of participants with plasma HIV-1 RNA <50 c/mL (c/mL) at Month 12 using the FDA Snapshot algorithm
- Proportion of participants with protocol-defined confirmed virologic failure (CVF) over time
- Proportion of participants with HIV-1 RNA  $\geq$  50 c/mL as per FDA Snapshot algorithm over time
- Absolute values and changes from Baseline in viral load and cluster of differentiation 4 (CD4+) cell counts over time

#### 7.2.2. Summary Measure

Number of subjects and percentage of participants with HIV-1 RNA < 50 c/mL at Month 12 (defined by the US FDA snapshot algorithm) will be presented by treatment group.

Number of subjects and percentage of participants with protocol-defined confirmed virologic failure (CVF) will be presented by treatment group and by visit.

Number of subjects and percentage of participants with HIV-1 RNA  $\geq$  50 c/mL (defined by the US FDA snapshot algorithm) will be presented by treatment group and by visit.

Descriptive statistics of the absolute values and changes from Baseline in viral load and cluster of differentiation 4 (CD4+) cell counts will be presented by treatment group and by visit.

#### 7.2.3. Population of Interest

The secondary efficacy analyses will be based on the Intent-to-Treat Exposed population, unless otherwise specified.

## 7.2.4. Strategy for Intercurrent (Post-treatment selection) Events

As defined by the snapshot algorithm, participants with last available HIV-1 RNA measurement < 50 c/mL while the participant is on treatment within the analysis visit window of interest are classified as HIV-1 RNA < 50 c/mL.

Participants without on-treatment HIV-1 RNA data for the visit of interest and who discontinue treatment for reasons not related to adverse event while having HIV-1 RNA  $\geq$  50 c/mL at time of discontinuation or who change study treatment not permitted per protocol before the analysis window are classified as having HIV-1 RNA  $\geq$  50 c/mL.

#### 7.2.5. Statistical Analyses / Methods

Details of the planned displays are provided in Appendix 12: List of Data Displays and will be based on GSK data standards and statistical principles.

Unless otherwise specified, endpoints / variables defined in Section 7.2.1 will be summarised using descriptive statistics, graphically presented (where appropriate) and listed.

## 7.3. Exploratory Efficacy Analyses

Table 3 provides an overview of the planned exploratory efficacy analyses. Details of the planned displays are provided in Appendix 12: List of Data Displays and will be based on GSK data standards and statistical principles. The exploratory efficacy analyses will be based on the Intent-to-Treat Exposed population, unless otherwise specified.

Table 3 Overview of Exploratory Efficacy Analyses

	Absolute			Change from Baseline				
Endpoints	Summary		Individual		Summary		Individual	
	Т	F	F	L	Т	F	F	Г
Plasma HIV-1 RNA over ti	me							
By visit	Y [1]		Y [2]	Y [3]	Y[1]			Y [3]
Target Detected vs								
Target Not Detected by	Υ			Y [5]				
visit [4]								
Confirmed Virologic Failu	re (CVF)	)						
CVF overall	Υ							
Plasma HIV-1 RNA at								
time of suspected and	Υ							
confirmed virologic failure								
CD4+ cell counts over time	ne							
Observed 	Υ				Υ			
HIV-1 conditions and dise	ase pro	gression	1					
HIV Conditions								
including/excluding	Υ			Υ				
Recurrences as recorded	Ī			I				
in eCRF								
HIV Disease	Υ							
Progressions 	1							

#### NOTES:

- T = Table, F = Figure, L = Listing, Y = Yes display generated.
- Summary = Represents TF related to any summaries (i.e. descriptive statistics) of data.
- Individual = Represents FL related to any displays of individual participant's data.
- 1. Using log10 transformed values.
- 2. Individual plasma HIV-1 RNA only for participants who are in the category of 'viral load ≥50 c/mL' at Month 12 per Snapshot algorithm or who are CVF participants. The figures will display all HIV-1 RNA values collected.
- 3. For CVF participant and, participants with viral load ≥ 50 c/mL during the Maintenance Phase.
- 4. See Section 12.6.3 for definition of "Target Detected" and "Target Not Detected", and for the specification of corresponding summary table.
- 5. Target Detected" and "Target Not Detected" are included in the listing for plasma HIV-1 RNA by visit.
- 6. Using available data without imputation for missing values.
- 7. See Section 12.6.3 for HIV disease progressions.

#### 8. SAFETY ANALYSES

The safety analyses will be based on the Safety population, unless otherwise specified.

#### 8.1. Adverse Events Analyses

Adverse events analyses including the analysis of adverse events (AEs), Serious (SAEs) and other significant AEs will be based on GSK Core Data Standards. The details of the planned displays are provided in Appendix 12: List of Data Displays.

#### 8.1.1. Injection Site Reactions

For the summary of Injection Site Reaction Adverse Events by Visit and Maximum Severity (Overall and by Common ISRs): ISRs will be assigned based on onset date to the most recent planned IM injection visit prior or equal to the AE onset date.

Maximum grade at each visit will be derived as the maximum grade among ISRs assigned to the particular visit, with consideration for whether the summary applies to a particular preferred term (vs. across preferred terms), or drug-related associated to CAB and/or RPV, or stratification by needle length (refer to Section 5.4.2).

Drug-related ISRs (based on investigator discretion) will be attributed to the causal agent (CAB vs. RPV) when this can be determined specifically based the side of injection administration and the side of the reported ISR (as collected in the eCRF). If we are unable to determine the causal agent in those cases where both drugs are given on one side and the ISR is reported non-specifically, then the attribution to a specific causal agent will remain unknown.

Common study drug ISR adverse events are defined by MedDRA preferred terms including injection site pain, injection site induration, injection site nodules and preferred terms of any other ISR with  $\geq$ 5% participants in the CAB LA + RPV LA arm, coming from study drug injections. The same set of common terms will be applied to 'overall' (CAB and/or RPV), CAB alone, RPV alone.

ISRs will be attributed to the needle length ( $\leq 1.5$ , > 1.5 to < 2,  $\geq 2$  inches) when this can be determined specifically based on the side of injection administration and the side of the reported ISR (as collected in the eCRF). If we are unable to determine the needle length in those events where both drugs are given on one side and their needle lengths are different, then the attribution to a needle length will remain unknown.

## 8.2. Clinical Laboratory Analyses

Laboratory evaluations including the analyses of chemistry laboratory tests, hematology laboratory tests, urinalysis, and liver function tests will be based on GSK Core Data Standards. The details of the planned displays are in Appendix 12: List of Data Displays.

#### 8.3. Adverse Events of Special Interest Analyses

Adverse events of special interest (AESI) are determined for CAB and/or RPV based on pre-clinical and clinical experience, along with information for the Integrase Inhibitor class of HIV medications and RPV safety profile. Table 4 shows the currently identified AESI, drug(s) of Interest and the reasons for inclusion. Changes to the MedDRA dictionary may occur between the start of the study and the time of reporting, and/or emerging data from on-going studies may highlight additional adverse events of special interest, therefore the list of AESIs may change at the time of reporting.

A summary by system organ class and preferred term will be provided for each of AESI. For Depression, anxiety and suicidal ideation/behaviour AESI, a summary by system organ class, maximum DAIDS toxicity grade and prior history will be provided. The details of the planned grouping and planned displays are provided in Section 12.10 and Appendix 12: List of Data Displays.

Table 4 Adverse Events of Special Interest

Adverse Events of Special Interest	Drug(s) of Interest	Reason for Inclusion
Hepatic Safety Profile: Assessment of Risk of hepatoxicity	CAB+RPV	Clinical, Class, Regulatory Interest, More prevalent in HIV population
Hypersensitivity Reactions (HSR)	САВ	Class, Regulatory Interest, Occurs in HIV population
Rash	RPV	Class, Regulatory Interest, Occurs in HIV population
Prolongation of the Corrected QT Interval of the ECG in Supratherapeutic Doses	RPV	Non-clinical, Clinical, Regulatory Interest
Suicidal Ideation/Behaviour	CAB+RPV	Clinical, Class, Regulatory Interest, More prevalent in HIV population
Depression	CAB+RPV	Clinical, Class, Regulatory Interest, More prevalent in HIV population
Bipolar Disorder	CAB+RPV	Clinical, Class, Regulatory Interest, More prevalent in HIV population
Psychosis	CAB+RPV	Clinical, Class, Regulatory Interest, More prevalent in HIV population

Adverse Events of Special Interest	Drug(s) of Interest	Reason for Inclusion
Mood Disorders	CAB+RPV	Clinical, Class, Regulatory Interest
Anxiety	CAB+RPV	Clinical, Class, Regulatory Interest
Sleep Disorders	CAB+RPV	Clinical, Class, Regulatory Interest, More prevalent in HIV population
Injection Site Reactions (ISR) from Study Drug Injections [1]	CAB+RPV	Clinical
Seizures and Seizure-like Events	CAB	Clinical, Regulatory Interest
Weight Gain	CAB	Clinical, Class
Rhabdomyolysis	CAB	Clinical, Class
Pancreatitis	CAB	More prevalent in HIV population
Impact on Creatinine	CAB+RPV	Regulatory Interest, Therapeutic Area, More prevalent in HIV population
Safety in Pregnancy	CAB	Regulatory Interest, Class

#### NOTE:

## 8.4. Other Safety Analyses

The analyses of non-laboratory safety test results including ECGs and vital signs will be based on GSK Core Data Standards, unless otherwise specified. The details of the planned displays are presented in Appendix 12: List of Data Displays.

ECG values of potential clinical importance are defined as a QTc of > 500 msec or increase from baseline in QTc  $\ge 60$  msec.

## 9. HEALTH OUTCOMES ANALYSES

## 9.1. Endpoint / Variables

- Change from Baseline (Day 1) in HIVDQoL at Months 6 and 12 (or Withdrawal)
- Change from baseline (Day 1) in total "treatment satisfaction" score, and individual item scores of the HIV Treatment Satisfaction Status Questionnaire (HIVTSQs) at Months 6 and 12 (or Withdrawal)

1. A separate analysis will be performed for ISRs from study drug injections as described in Section 8.1.1.

- Change in treatment satisfaction over time using the HIV Treatment Satisfaction Change Questionnaire HIVTSQc at Month 12 (or Withdrawal).
- Preference between injections of LA HIV treatment and daily oral HIV treatment at Month 12. This is an exploratory endpoint.
- Reasons for switching to injectable HIV treatment at Baseline (Day 1). This is an exploratory endpoint.

## 9.2. Summary Measure

Summary statistics of the above endpoints will be presented by treatment group.

#### 9.3. Population of Interest

The health outcomes outputs will be based on the Intent-to-Treat Exposed population, unless otherwise specified.

## 9.4. Strategy for Intercurrent (Post-treatment selection) Events

No imputations would be performed for any missing data.

#### 9.5. Statistical Analyses / Methods

Details of the planned displays are provided in Appendix 12: List of Data Displays and will be based on GSK Data Standards and statistical principles.

Unless otherwise specified, endpoints / variables defined in Section 9.1 will be

summarised using descriptive statistics, graphically presented (where appropriate) and listed.

#### 10. VIROLOGY

The virology analyses will mainly use genotype and phenotype data based on plasma sample for CVF population, unless otherwise specified. Additional analyses for HIV-1 resistance may be carried out on peripheral blood mononuclear (PBMC) samples collected at Day 1 or Withdrawal.

If pre-treatment genotypic/phenotypic results are available from both the central laboratory and Monogram Biosciences, then Baseline genotype/phenotype will be determined based only upon the data provided by Monogram assays.

Table 5 Overview of Planned Virology Analyses

		Absolute								
Endpoints	Sun	nmary	Individual							
	Т	F	F	L						
Genotypic resistance at time of CVF 	·									
Prevalence of Resistance Mutations	Y[2]			Υ						
Prevalence of Genotypic Susceptibility	Y									
Phenotypic resistance at time of CVF 	.	•	•	•						
Prevalence of Phenotype	Y[3]			Υ						

	Absolute									
Endpoints	Sum	mary	Individual							
	T	F	F	L						
Fold Change to CAB and RPV	Υ			Y [4]						
IN, PR/RT Replication Capacity				Υ						
Other										
Viral load, Genotypic and Phenotypic data for										
Participants with genotype and/or phenotype data				Y [4]						
for CVF participants										
Net Assessment	Υ									

#### NOTES:

- T = Table, F = Figure, L = Listing, Y = Yes display generated.
- Summary = Represents TF related to any summaries (i.e. descriptive statistics) of the observed raw data.
- Individual = Represents FL related to any displays of individual participant observed raw data.
- 1. For the CVF as indicated by two consecutive plasma HIV-1 RNA levels ≥200 c/mL after prior suppression to <200 c/mL, the first visit of these two consecutive visits is defined as 'the suspected visit', and the 2nd one is the confirmed visit. Sample used for resistance testing is taken at the suspected visit, and only tested once a participant confirms virological failure at a subsequent visit. If the test fails with the sample at the suspected visit, we will just report it as 'no data'. The sample from the confirmed visit may be used for exploratory analyses.

- No. and percentage of participants with IN resistance mutations or major mutations in the classes of NNRTI, NRTI, PI, respectively, as defined in Section 12.6.6.
- 3. Separate outputs by phenotypic susceptibility and by number of drugs to which participants are phenotypic resistant or partial sensitive or sensitive.
- 4. Fold change to CAB and RPV will be included in the listing for viral load, genotypic and phenotypic data for participants with genotype and/or phenotype data for CVF and non-CVF participants.

#### 12. APPENDICES

# 12.1. Appendix 1: Protocol Deviation Management and Definitions for Per Protocol Population

#### 12.1.1. Exclusions from Per Protocol Population

Important protocol deviations leading to exclusion from the Per Protocol population are those deviations which may

- i. directly impact the efficacy endpoint of HIV-1 RNA; or
- ii. lead to permanent discontinuation of IP/withdrawal and hence indirectly impact the efficacy endpoint by causing data to be missing.

The following criteria define the protocol deviations which, if they occur prior to an analysis timepoint of interest (e.g. Month 12), will lead to exclusion of a subject from the Per-Protocol population for that analysis. Potential protocol deviations leading to exclusion from PP population will be reviewed by the study team to confirm that they meet these criteria. A final review will occur before the clinical database has been frozen for analysis.

A subject meeting any of the following criteria will be excluded from the Per Protocol population based on case-by-case clinical determination:

Number	Exclusion Description
01	Participant deviates from any inclusion or exclusion criteria that may significantly affect exposure, response to therapy or participant safety or that are fundamentally inconsistent with the intended study population, as recorded in the Protocol Deviation form in the eCRF based on study team review (where indicated in the PDMP as case-by-case determination).
02	Participant has maintenance phase non-compliance (including IM dosing errors) with investigational product up to an analysis timepoint of interest, meeting one of the following conditions:  1. Month 12 analysis only:  • Q2M arm: two or more injection intervals affected by over dosage deviations (e.g. extra injection or excessive volume administered, length of time between injections less than 7 weeks, excluding split doses).  2. ≥10% of total time on-treatment with under dosing deviations. The percentage of total time on-treatment with under dosing deviations will be calculated by (the total number of non-compliant dosing days / the total number of intended exposure days) * 100%.  Number of Intended Exposure Days = Date of Last Viral Load – Start Date of Study Treatment + 1, where the last viral load refers to the last on-treatment viral load up to Study Day 360 for Q2M arm and study day of last nominal Month 12 visit for DTG + RPV arm during maintenance phase for Month 12 analysis.

Number	Exclusion Description							
	The total number of non-compliant dosing days up to the analysis timepoint visit (or date of IP discontinuation/withdrawal, whichever is earlier), is derived as follows (summing across all instances):  • Q2M arm:							
	
 
Length of time (in days) until next injection from date of dosage deviation (e.g. 2 mL administered instead of 3 mL).
 
Length of time (in days) in excess beyond 67 days between injections.
 
Length of time (in days) in excess beyond 67 days from last injection until start of oral bridging post Month 4.
 
Interrupted days in oral bridging if the oral dose has been interrupted for 3 or more consecutive days and the primary interruption reason is not adverse event or laboratory abnormality (based on the eCRF Exposure forms). 3 days will be assumed if such interrupted days are not available in the database.
 
DTG + RPV arm: Durations of interruptions for reasons other than treatment-related adverse events or laboratory abnormalities (based on
 
							
	Exposure eCRF forms).							
03	Prohibited medications: receiving ART medication other than that prescribed/allowed by the study (excluding permanent changes in ART regimen; such cases will be retained as 'HIV1-RNA ≥50 c/mL' in the per protocol snapshot analysis) or receiving prohibited concomitant medication that would impact exposure or response to therapy with duration and route of administration taken into consideration, as recorded in the Protocol Deviation form in the eCRF based on study team review (where indicated in the PDMP as case-by-case determination).							
04	Permanent discontinuation of IP/withdrawal due to a reason of "Protocol Deviation" (as recorded in the eCRF).							
05	Other important protocol deviations that exclude Participant from Per protocol population as recorded in the Protocol Deviation form in the eCRF based on study team review (where indicated in the PDMP as case-by-case determination).							

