## 12.3.2. Definitions of Assessment Windows for Data Other than Health Outcomes

Table 6 Assessment Windows for Screening and Maintenance Phase Data for CAB LA + RPV LA arm

All Parameters (except for where noted)	Target Study Day	Analysis Window	Analysis Timepoint
	1	Baseline information to be collected at nominal visit Day 1 which is the last available recorded value up to and including the Maintenance treatment start	Baseline

All Parameters (except for where noted)	Target Study Day	Analysis Window	Analysis Timepoint
		date, excluding 2-hour post-dose ECG taken on the Maintenance treatment start date	
	1	Date of first maintenance dose of IP+	Day 1
	31	2 ≤ Study Day ≤ 60	Month 2*
	91	61 ≤ Study Day ≤ 120	Month 4
	151	121 ≤ Study Day ≤ 180	Month 6
	211	181 ≤ Study Day ≤ 240	Month 8
	271	241 ≤ Study Day ≤ 300	Month 10
	331	301 ≤ Study Day ≤ 360	Month 12
	391	361 ≤ Study Day ≤ 420	Month 14
	451	421 ≤ Study Day ≤ 480	Month 16
	511	481 ≤ Study Day ≤ 540	Month 18
	571	541 ≤ Study Day ≤ 600	Month 20
	631	601 ≤ Study Day ≤ 660	Month 22
	691	661 ≤ Study Day ≤ 720	Month 24
	751	721 ≤ Study Day ≤ 780	Month 26
	(( m -1)*30)+1	$(((m-1)*30)-29) \le \text{Study Day} \le (((m-1)*30)+30)$	Month m , m =28, 30,
If a	If a participant permanently discontinued study treatment:		
NOTES		Date > max (Date of Last Oral Dose of CAB+RPV + 1, Date of Last Injection + 67)	Follow-up#

Table 7 Assessment Windows for Screening and Maintenance Phase Data for DTG + RPV arm

All Parameters (except for where noted)	Target Study Day	Analysis Window	Analysis Timepoint
	1	Baseline information to be collected at nominal visit Day 1 which is the last available recorded value upto and including the Maintenance treatment start date, excluding 2-hour post-dose	Baseline

+ Only non-baseline records from the mentioned assessment window will be assigned to Day 1.

\* The second loading injections will be administered 1 month (Month 2 visit, start of the second month of the study) after initial loading dose (CAB LA 600 mg + RPV LA 900 mg), with subsequent injections (CAB LA 600 mg + RPV LA 900 mg) occurring every 2 months thereafter.

# Follow-up will be derived only for participants who permanently discontinued study treatment.

All Parameters (except for where noted)	Target Study Day	Analysis Window	Analysis Timepoint
		ECG taken on the Maintenance treatment start date	
	1	Date of first maintenance dose of IP+	Day 1

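### SAP criterion 02 for the per-protocol population has no rule for the 30-day loading interval, so, read literally, a skipped second loading dose counts for less than a partial one

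*SAP*

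**What the plan says.** SAP Section 12.1.1, criterion 02, defines dosing non-compliance in the Q2M arm in two ways.

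- **Over-dosing (Month 12 analysis only).** The trigger is "two or more injection intervals affected by over dosage deviations". One listed example is "length of time between injections less than 7 weeks". Split doses are the only exemption.
- **Under-dosing.** The trigger is "≥10% of total time on-treatment with under dosing deviations". The numerator includes "Length of time (in days) in excess beyond 67 days between injections". A separate bullet counts every day from a dosage deviation to the next injection, with a partial volume as its example. The denominator is "Number of Intended Exposure Days = Date of Last Viral Load – Start Date of Study Treatment + 1", using "the last on-treatment viral load up to Study Day 360 for Q2M arm".

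Only the bullet on the gap before oral bridging is restricted in time (after Month 4). The bullet on time between injections is not.

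The same SAP plans a shorter first interval. The note to Table 6 in Section 12.3.2 says: "The second loading injections will be administered 1 month (Month 2 visit, start of the second month of the study) after initial loading dose". Section 12.3.1 puts Month 2 on Day 31 and Month 4 on Day 91. Section 12.6.2 gives a single planned interval of 60 days for the whole arm.

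Section 12.1.1 also says that the study team reviews potential deviations before freeze and that exclusion is a case-by-case clinical judgement. Criterion 05 allows exclusion for other important deviations.

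**The concern.** Both interval limits are built around 60 days, and neither fits a planned interval of 30. On the long side, an upper limit of 67 days gives the second loading dose 37 days of slack beyond its due date. Protocol Sections 4.2.2 and 6.8.1.1 hold that dose to a tighter window than any later one. Most of the lateness of a missed second loading dose is therefore never counted. On the short side, an on-time second loading dose falls under the 7-week limit.

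The per-protocol Snapshot table (SAP Section 12.12.5, Table 2.02) is the only table of the Month 12 Snapshot outcome in an alternative population, so who belongs in it should follow a consistent rule. Protocol Section 4.4.1.2 treats the second dose as relevant to exposure: the predicted median RPV trough is 40 ng/mL before a second dose at Week 4, against 30 ng/mL observed before a second dose at Week 8. Counts will be small. At the 3% of 100 used in protocol Section 10.2.1, three participants fail, and removing one of them moves the estimate from 3/100 = 3.0% to 2/99 = 2.0%.

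**Working it through.** **Inputs.** Target day for Month m is (m − 1) × 30 + 1, giving Days 31, 91, 151, 211, 271 and 331 (SAP 12.3.1). The Month 2 window is −7 to 0 days, and later windows are ±7 days (protocol 4.2.2). Windows are anchored to dates projected from Day 1 (footnote k, SAP 12.2.1). The thresholds are those in criterion 02.

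**The plan's own limits.** 67 = 60 + 7, the maintenance interval plus its window. 7 weeks = 49 days = 56 − 7, whereas the SAP's own 60-day interval less 7 would give 53.

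**Under-dosing, Month 2 dose skipped, Month 4 on Day 91, last viral load on Day 331.**

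- Gap: 91 − 1 = 90 days.
- Counted days: 90 − 67 = 23.
- Share: 23/331 = 6.9%, below 10%, so retained under the interval bullet.

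Over the in-window Month 4 dates:

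| Month 4 day | Gap | Days over 67 | Last VL Day 301 | Day 331 | Day 360 |
|---|---|---|---|---|---|
| 84 | 83 | 16 | 5.3% | 4.8% | 4.4% |
| 91 | 90 | 23 | 7.6% | 6.9% | 6.4% |
| 98 | 97 | 30 | 9.97% | 9.1% | 8.3% |

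Every cell is below 10%. Two conditions apply.

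- The table assumes that no later interval exceeds 67 days. Windows permit up to 60 + 7 + 7 = 74 days. With injections on Days 91, 144, 218, 264 and 338, the count is 23 + 7 + 7 = 37, and 37/338 = 10.9%.
- With Month 4 on Day 91, the threshold is also reached if the last viral load is on or before Day 230 (23/230 = 10.0%).

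**Comparators in the same criterion, other doses on target.**

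- Partial volume at Month 2: 91 − 31 = 60 days; 60/331 = 18.1%, excluded.
- Month 6 skipped: (211 − 91) − 67 = 53 days; 53/331 = 16.0%, excluded.

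**Over-dosing.** On-schedule intervals are 30, 60, 60, 60, 60 and 60 days. One is under 49 and two are needed, so nobody is excluded on this ground alone. The Month 2 to Month 4 interval cannot be short inside the windows (84 − 31 = 53). For two consecutive maintenance injections with offsets a and b, the interval is 60 + b − a. It is under 49 when a − b is at least 12, which holds for 6 of the 15 × 15 = 225 pairs and gives 46 to 48 days. Example: Month 4 on Day 98 and Month 6 on Day 144 are both in window and 46 days apart. Added to the loading interval, that makes two.

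The documents give no timing distribution, so the share affected is illustrative only:

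| Assumed timing inside windows | At least one 46–48 day interval by Month 12 | Leaving out Month 10–12 |
|---|---|---|
| Uniform | 10.5% | 7.9% |
| Normal, SD 3 days, clipped | 0.8% | 0.6% |
| Normal, SD 5 days, clipped | 10.9% | 8.3% |

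The last column is shown because Section 12.1.1 counts deviations before the timepoint, and the Month 10–12 interval closes only with the Month 12 injection. If the loading interval were not counted, the uniform case by Month 12 would fall to 0.2%.

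**After the change.** Counting the skipped dose from 30 days gives 60/331 = 18.1%; from 37 days (if the window runs to +7), 53/331 = 16.0%. Over Month 4 on Days 84–98 and last viral load on Days 301–360, the range is 46/360 = 12.8% to 67/301 = 22.3%, always above 10%.

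**The case against.** The SAP never says outright that these limits govern the loading interval. That is inferred from the absence of an exemption. Criterion 02 concerns non-compliance and speaks of deviations, and a second dose given on its planned date is neither. Reviewers confirm each case before freeze, decide case by case, and work from a deviation management plan not available here. A skipped loading dose could be treated as a dosage deviation running from Day 31 (60 days, 18.1%), or removed under criterion 05. The over-dosing scenario needs near-opposite window extremes, and its frequency rests on timing assumptions with no source in the documents. The analysis is descriptive, and the primary result is on ITT-E.

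Most of this stands and limits the over-dosing half to a clarification. It does not dispose of the under-dosing half. There the rule is numeric, its neighbouring bridging bullet shows that a time restriction was written where one was wanted, and the result is inconsistent: no dose counts for less than a partial dose at the same visit. Discretion could repair this, but the team's stated task is to confirm that cases meet the criteria. In an open-label study it is better not to depend on overriding them.

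**Conclusion.** Criterion 02 needs a rule for the loading interval. The main defect is on the under-dosing side. Read literally, the interval bullet counts 6.9% for a wholly skipped Month 2 dose (4.4% to 9.97% over in-window Month 4 dates with a last viral load on Days 301–360 and no later interval beyond 67 days), while a partial Month 2 dose or a skipped Month 6 dose passes 10%. The over-dosing side is secondary: the planned loading interval consumes one of two allowances, and the share of in-window participants who would then meet the rule is anywhere from about 0.6% to 11%, depending on assumed timing.

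A reader might infer three stronger things that the documents do not support.

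- That following the schedule leads to exclusion as over-dosed: the loading interval alone excludes nobody, and review may set aside the flag.
- That a participant who skips the loading dose is certain to stay in: criterion 05, case review, the dosage-deviation bullet or later long intervals could each lead to exclusion.
- That the trial's main result is compromised: only Table 2.02 is touched, and Tables 2.03 and 2.04 also report the endpoint in ITT-E.

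**What to change.** Amend SAP criterion 02 before database freeze:

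1. State that the planned Day 1 to Month 2 interval, any re-loading interval directed by the Medical Monitor, and any interval with both injections inside their protocol windows are not over-dosage deviations.
2. For the loading interval, count under-dosing days from the end of the protocol's own Month 2 window instead of from 67 days, and say that a wholly missed second loading dose is counted this way.

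The second change needs one prior step. Protocol Sections 4.2.2 and 6.8.1.1 give the Month 2 window as −7 days up to the projected date (6.8.1.1 adds a preference against going later), whereas footnote k of the schedule (protocol Sections 1.3 and 8.1.1, SAP Section 12.2.1) gives ±7 days without excepting Month 2. These passages must be reconciled. No dosing rule is proposed here, and the skipped-dose result exceeds 10% under either statement.

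The cost is SAP wording and a small programming change. No new data are needed.
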